Control: This is a pilot proof of concept study with sample size insufficient for a formal randomized comparison. In order to have a valid comparator, participants will be randomly allocated to an intervention and control group (approx. 40 per group). No p values will be calculated. Comparisons will be as risk ratios or mean differences with 95% confidence intervals.

Outcomes

Baseline demography and clinical data will be recorded.

Primary: The primary outcome is the combined frequency of adverse device effects and device deficiencies up to discharge from hospital.

Adverse device effects (ADEs) encompass any adverse event with a reasonable causal relationship resulting from insufficient or inadequate instructions for use; problems with the deployment, implantation, installation, or operation of the device; malfunction of the device; or user error or intentional misuse of the device. They will include device deficiencies such as device expulsion / falling out of the uterus, failed maintenance of suction pressure and tube blockage.

A Serious Adverse Device Effect (SADE) is an adverse device effect that has resulted in any of the consequences characteristic of a serious adverse event. An example of this would be the need for further intervention to treat trauma caused by the device (e.g. sutures, laparotomy, etc).

Secondary efficacy outcomes will include:

- 1. Measured blood loss within 30 minutes after insertion (ml)
- 2. Blood loss >500ml
- 3. Blood loss >1000ml
- 4. Efficiency of suction (assessed through ultrasound assessment of residual blood in the uterus at 30 minutes or blood expressed from the uterus after tube removal)
- 5. Blood pressure, pulse and shock index 15 minutes after vaginal birth or caesarean
- 6. Change in routinely collected haemoglobin levels pre delivery to post delivery
- 7. Blood transfusion
- 8. ICU admission
- 9. Death
- 10. Functionality and acceptability:
 - a. Active bleeding from the uterus continuing for more than 10 minutes (main efficacy outcome).
 - b. Any adverse event
 - c. Pain experienced (No pain/Mild /Severe/Unbearable)
 - d. Need for Additional interventions to stop bleeding (e.g. more uterotonics, compressive measures, UBT, laparotomy, hysterectomy)
 - e. Was STUT effectively inserted? (Yes/No/Unknown)
 - f. How easy was it for health care providers to insert the Suction Tube Uterine Tamponade (easy/moderately difficult/Difficult/failed)

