The clinical trial will include use of personal demographic and clinical information of participants. The information will be de-identified using a trial ID number and stored in a password-protected computer. Paper trial documents will be stored under lock and key.

Data analysis

Data management will be conducted by the Liverpool University Clinical Trials Unit. The locked database will then be passed to the investigators for analysis.

For continuous variables, the number of participants, number of missing values, minima, maxima, means and standard deviations will be reported, with 95% confidence intervals. If distribution is not normal, medians and interquartile range (IQR) will be reported.

For categorical variables, the number of participants, number of missing values and percentages will be reported, with 95% confidence intervals.

Comparisons will be expressed as risk ratios or mean differences with 95% confidence intervals. As the study is not powered for statistical analysis, no p values will be reported.

Data sharing and access

Data will be made available after publication of results on reasonable request based on an ethically approved research protocol. Data sharing is included in the participant information.

Trial registration

The protocol will be registered with SANCTR and ISRCTN.

Research team

[name] is a senior researcher with expertise in clinical trials. **[name]** is a researcher with many years' experience conducting non-regulatory and regulatory clinical trials

The Trial Management Group will be responsible for governance and oversight. [name] will be overall responsible for the clinical trial conduct, whilst [name] will supervise the clinical trial.

Facilities

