	11.	\bigcirc *Insertion of tube; \bigcirc easy, \bigcirc moderately difficult, \bigcirc difficult, \bigcirc Failed, \bigcirc not done
	12.	Alternative Management
	13.	*Time tube insertion procedure completed 24 hr: H H : M M
	14.	*Check tube/balloon stable in uterus Yes / No / Onot used
	15.	Ocontinue routine care including repair of bleeding tears
	16.	*Effect of device on exam/mx of lower genital tract bleeding? Facilitated; Interfered; Neither; Unknown
	17.	○ Note the time per vaginal bleeding stopped. 24 hr: H H : M M
	18.	○ 15 minutes after insertion (10 above) note time 24 hr: H H : M M
		Systolic BP Diastolic Pulse
	19.	○ 30 minutes after insertion, note time. 24 hr: H H : M M
	20.	
		ml ml
	21.	Replace empty tray, expel blood from the uterus by fundal massage (into tray)
	22.	○ Measure blood loss in tray = RESIDUAL
		ml ml
	23.	*disconnect suction. If no bleeding in 10 minutes, remove U=STAT tube
	2/	*If bleeding continues replace empty tray continue suction plus other measure

25. When bleeding stopped, measure blood loss in tray = Secondary blood loss
ml ml
26. *Measure blood loss in suction bottle
ml ml
27.
○ None
The participants will be followed till discharge and the outcome data, as well as any complications, recorded.

Caesarean birth Clinical checklist (remains in hospital records)

Equity for Suction Tamponade Access to treat postpartum haemorrhage: The ESTA project

	1.	○ Consent signed
	2.	Oconfirm with Mother that still happy with consent
	3.	OStudy trolley is available with register, U-STAT suction tubes, working suction
	4.	Clean drape or Maternawell tray available for post-op use
	5.	○ Manual suction device ready with vacuum pumped or suction machine pressure set to 100mmHg – block tubing to check
	6.	\bigcirc After birth of baby, open next numbered envelope and note allocation: \bigcirc STUT* \bigcirc Control
Aft	er p	placenta delivered completely:
	7.	○ Note the time, 24 hr: H H : M M
	8.	\bigcirc *Insert U-STAT tube to fundus of uterus and lower end through cervix and vagina, ask assistant to connect and start suction
	9.	\bigcirc *Insertion of tube; \bigcirc easy, \bigcirc moderately difficult, \bigcirc difficult, \bigcirc Failed, \bigcirc not done
	10.	. Alternative Management
	11.	. *Time tube insertion procedure completed 24 hr: H H : M M
	12.	. Continue uterine closure
	13.	*Effect of device on visualisation for uterine closure? \(\text{Facilitated}; \text{Interfered}; \) Neither; \(\text{Unknown}\)

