	14.	. Time uterus closed 24 hr: H H : M M
	15.	. Measure blood volume in suction bottle = pre-suction volume:
		ml ml
	16.	*Note the time bleeding through suction tube stopped. 24 hr: H H : M M
	17.	. O 15 minutes after placental delivery (7 above) note time 24 hr: H H : M M
		Systolic BP Diastolic Pulse
	18.	. After skin closure, estimate surgical blood loss (excluding U=STAT tube drainage)
		ml ml
	19.	. O In recovery room: Place drape or Maternawell tray under participant's buttocks
	20.	
	21.	. O 30 minutes after placental delivery (7 above), note time. 24 hr: H H : M M
	22.	. Swab vagina and measure blood loss in drape/tray = postop blood blood

23. O Place new tray or drape under participant and express blood from uterus -
Measure blood loss in drape/tray = RESIDUAL blood
ml ml
24. *Disconnect suction, if no bleeding after 10 minutes, remove U-STAT tube. If
bleeding resumes, reconnect suction and manage as per hospital protocol
25. *Measure blood loss in suction bottle
ml ml
26. *Suction tube problems: Fell out; blocked; leaking; Poor suction
○ None

ml

The participants will be followed till discharge and the outcome data, as well as any complications, recorded.

Participant questionnaire (Vaginal birth Intervention group only)

Protocol Title: Equity for Suction Tamponade Access to treat postpartum haemorrhage: The ESTA project			
Site Number:	Subject ID:	Date:(dd/mmm/yy)	
Dear Participant, thank you for assisting us with the ESTA project. Pease would you answer the following questions. There are no right or wrong answers. Please just give us your personal opinions. Please feel free not to answer if you prefer not to.			
Questionnaire		Comment/Notes	
*After the hirth of your ba	by a tubo was	T	
*After the birth of your baby, a tube was inserted to your uterus to help reduce bleeding Please could you describe the pain you experienced? 0=No pain; 1 = Mild pain; 2 = Severe pain; 3 = Unbearable pain; 4 = unsure; 9 = no data			
*Please could you describe when the tube was removed = Mild pain; 2 = Severe pain Unbearable pain; 4 = unsure	d? 0=No pain; 1 u; 3 =		
*Please could you describe overall about the suction tub 0= fine; 1 = uncomfortable b = Unacceptable; 3 = Unbear unsure; 9 = no data	pe procedure? out acceptable; 2		
Thank you for assisting with this questionnaire			

Date completed

(dd/mmm/yy)

Completed by (initials):

Participant questionnaire (Caesarean birth Intervention group only)

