Protocol Title: Equity for Suction Tamponade Access to treat postpartum haemorrhage: The ESTA project			
Site Number:	Subject ID:		Date:(dd/mmm/yy)
Dear Participant, thank you for assisting us with the ESTA project. Pease would you answer the following questions. There are no right or wrong answers. Please just give us your personal opinions. Please feel free not to answer if you prefer not to.			
Questionnaire			Comment/Notes
D : 4			
During the caesarean operation, a tube was inserted to your uterus to help reduce bleeding. Please could you describe the pain you experienced from the tube? 0=No pain; 1 = Mild pain; 2 = Severe pain; 3 = Unbearable pain; 4 = unsure; 9 = no data			
Please could you describe how you felt when the tube was removed? 0=No pain; 1 = Mild pain; 2 = Severe pain; 3 = Unbearable pain; 4 = unsure; 9 = no data			
Please could you describe how you felt overall about the suction tube procedure? 0= fine; 1 = uncomfortable but acceptable; 2 = Unacceptable; 3 = Unbearable; 4 = unsure; 9 = no data			
Thank you for assisting with this questionnaire			

Completed by (initials):	Date completed	(dd/mmm/yy)
--------------------------	----------------	-------------

Health care provider questionnaire (Vaginal birth Intervention group only)

Protocol Title: Equity for Suchaemorrhage: The ESTA p	=	cces	s to treat postpartum
Site Number:	Subject ID:		Date:(dd/mmm/yy)
Dear Health care provider, thank you for assisting you answer the following questions. There are no give us your personal opinions. Please feel free			nt or wrong answers. Please just
Questionnaire			Comment/Notes
After birth of the baby and placenta, how easy was it to insert the suction tube in the uterus? 0=Easy; 1 = Difficult; 2 = Very difficult; 3 = not possible; 4 = unsure; 9 = no data			
Was the suction tube stable in the uterus? 0=No; 1 = Stable; 2 = fell out; 3 = not used; 4 = unsure; 9 = no data			
Did the suction tube leak air Leaked a little; 2 = leaked a = unsure; 9 = no data	•		
Did the suction tube get blockled and cleared; 2 = blockled removed; 3 = not used; 4 = data	ocked had to be		
Did the suction tube appear uterine contraction and redu 0=No; 1 = A little; 2 = A lot; 3 unsure; 9 = no data	icing blood loss?		
Was the suction tube easy t 1 = A little difficult; 2 = Very used; 4 = unsure; 9 = no da	difficult; 3 = not		
Please could you describe habout the suction tube procenegative; 1 = Positive; 2 = N; 9 = no data	edure? 0=		

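### Pain (secondary outcome 10c) is listed without limit to the device arm but is collected only there, and the vaginal and caesarean forms ask the main pain question differently

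*Protocol*

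**What the plan says.** Under Outcomes, the secondary efficacy outcomes include item 10 (functionality and acceptability), of which 10c is "Pain experienced (No pain/Mild /Severe/Unbearable"). No arm is named. The Control paragraph says that women are randomised so that there is a valid comparator. The Data analysis section adds: "Comparisons will be expressed as risk ratios or mean differences with 95% confidence intervals". Under Procedures, participants in general, with no arm specified, are said to complete questionnaires covering discomfort among other things.

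The forms are narrower. One is headed "Participant questionnaire (Vaginal birth Intervention group only"), the other "Participant questionnaire (Caesarean birth Intervention group only"). The main pain question on the vaginal form reads "inserted to your uterus to help reduce bleeding Please could you describe the pain you experienced"; on the caesarean form it reads "Please could you describe the pain you experienced from the tube". Both forms also have a removal item, "Please could you describe how you felt when the tube was removed", answered on the same pain levels.

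In the vaginal birth checklist the tube goes in at item 10, item 15 continues "routine care including repair of bleeding tears", item 21 empties the uterus by fundal massage, and removal comes at item 23.

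**The concern.** There are two separate problems.

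First, an outcome listed for a randomised comparison has no data source in one of the two arms. A statistical analysis plan could declare the outcome descriptive, but it could not recover answers that were never asked for.

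Second, the device-arm answers do not all mean the same thing. A woman who has had tears repaired and her uterus massaged while the tube was in place, and who is then asked about the pain she experienced, may reasonably report all of it. Without a control group asked the same question, there is nothing to show how much pain would have been present anyway.

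Acceptability is one of the stated purposes of this proof-of-concept trial, and pain during insertion is a row of the target product profile (Table 1). The trial is also meant to show whether a substantive randomised trial is suitable. A pain result that cannot be set against the comparator, and that was asked differently by mode of birth, serves those purposes poorly.

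**Working it through.** The plan states no figure for pain, so there is none to reproduce. The check is a comparison of the outcome list with the data-collection forms.

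**Step 1: where pain is recorded.**

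| Source | Pain item? | Arm |
|---|---|---|
| Participant questionnaire, vaginal birth | Yes (main question and removal) | Intervention only |
| Participant questionnaire, caesarean birth | Yes (main question and removal) | Intervention only |
| Case record form | None readable | Both |
| Vaginal and caesarean clinical checklists | None readable | Both |
| Health care provider questionnaires | None | Asks about the tube, not about the woman's pain |

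The readable case record form jumps from item 23 to item 25. The neighbouring items concern air leak and the effect of the device on examination, so nothing suggests that a pain item stood there, but the text cannot exclude it.

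**Step 2: what can be estimated.** A risk ratio is (x1/n1)/(x0/n0), where n0 is the number of control women with a pain answer. Here n1 is about 40 and n0 = 0, so the ratio is undefined. The same holds for a mean difference. Only the device-arm proportion x1/n1 is available.

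**Step 3: how precise that proportion is.** At least 25% of the 40 device participants must come from each mode, that is 0.25 × 40 = 10. Exact (Clopper-Pearson) 95% intervals for illustrative counts are below; with x = 0 the upper limit is 1 − 0.025^(1/n).

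| Women reporting the outcome | 95% interval |
|---|---|
| 0 of 40 | 0 to 8.8% |
| 4 of 40 | 2.8 to 23.7% |
| 0 of 10 | 0 to 30.8% |
| 1 of 10 | 0.3 to 44.5% |

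These describe the device arm only and say nothing about the contrast with control.

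**Step 4: the wording by mode.** The caesarean question limits the pain to that caused by the tube. The vaginal question names the tube in its lead-in sentence but then asks about pain without that limit. By the checklist order (items 10, 15, 21, 23), tear repair and fundal massage both fall between insertion and removal. The removal item is the same on both forms and concerns the tube.

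**Step 5: whether 10c is meant for the device arm alone.** Items 10e to 10k concern the tube and can be answered only where it was used. Items 10a, 10b and 10d apply to both arms. Item 10c names no device, so its wording places it with the second group, while the forms place it with the first.

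**The case against.** The best defence is that 10c was always meant as a descriptive acceptability measure. It stands under functionality and acceptability among several device-only items. The sentence on risk ratios says how comparisons are expressed, not that every outcome is compared. The protocol also calls its sample insufficient for a formal randomised comparison and reports no p values. That reading is plausible, and it is why the fix offers a descriptive option. But the protocol nowhere says so, and its general statement on questionnaires does not match the form headings.

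It can also be said that the claimed advantage in pain is over balloon devices and Jada, neither of which is assigned to the control arm. That stands. A control item would measure background pain after birth and would not test the claim against bulkier devices.

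A reader might infer more than the documents support:

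- **That the pain data cannot be attributed to the device at all.** The caesarean question and the removal item on both forms name the tube, and the vaginal question follows a sentence about it. Only the main vaginal item is loose.
- **That caesarean answers are mostly uninformative because of anaesthesia.** The protocol does not describe anaesthesia. The caesarean question is not limited to the moment of insertion, and the tube stays in through the recovery-room steps.
- **That a pooled pain rate would follow the mix of modes.** No pooling is stated. The forms are separate by mode, randomisation is stratified by mode, and reporting by mode can be left to the analysis plan.
- **That the absence of a moderate level invalidates the scale.** It makes the scale coarse, but the forms also offer an unsure code, a comment column and freedom not to answer. This is mainly a preference about the scale.

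**Conclusion.** The point holds in this limited form. As the forms stand, the control arm supplies no pain answers, so outcome 10c cannot be compared between arms. The main pain question also differs by mode, and the vaginal version is open to background pain from procedures done while the tube is in place. What remains is a device-arm description with wide intervals, especially within one mode of birth.

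The conclusion rests on the readable text of the forms and assumes that no pain item was lost from the case record form or checklists. It depends on no assumed pain rate. The size of any background contribution to the vaginal answers is unknown, and the documents give no basis for estimating it. The finding concerns one secondary outcome and leaves the primary safety outcome untouched. It is still worth correcting, because the change is small and answers not collected during the hospital stay cannot be supplied at analysis.

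**What to change.** 1. Add one pain item, worded identically for both arms, covering a fixed period after delivery of the placenta. Use it for the between-arm comparison in 10c.
2. On the vaginal form, add the words *from the tube* to the main pain question so that it matches the caesarean form.
3. Keep the existing removal items as they are.
4. Report device-arm tube pain by mode of birth.
5. Optionally, add a moderate level to the scale.

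If control data are not wanted, state in Outcomes that 10c is descriptive in the device arm only, and align the questionnaire statement under Procedures with the form headings. Item 2 should be done in either case.

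The cost is about 40 one-question responses from control women, the same question added to the device-arm forms, and a few words on the vaginal form. The downside is slight extra data collection.

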Protocol

Equity for Suction Tamponade Access to treat postpartum haemorrhage: The ESTA project

Sponsor

Wits Health Consortium

CI

[name]

Synopsis

Emerging evidence suggests that uterine suction tamponade is more effdective than balloon tamponade. The currently available registered device (Jada) is unaffordable in LIMCs. We propose to conduct 'proof of concept' clinical testing of a purpose-designed, affordable device among 40 consented participants at risk of postpartum haemorrhage following vaginal or caesarean birth. Evaluation will include a randomly allocated (1:1) control group.

Context

Excessive bleeding after childbirth (postpartum haemorrhage, PPH) causes many deaths worldwide, most of which are avoidable with proper treatment. PPH usually occurs because the womb (uterus) does not contract enough after birth to compress the bleeding vessels. When medical methods fail, standard care has been to insert a balloon into the uterus and inflate it with saline. A recent development has been to replace this balloon with a suction catheter which assists uterine contraction thus stopping the bleeding. There is increasing evidence that this is more effective than a balloon, and in the USA, the FDA-approved Jada suction device has become the mainstay of treatment for persistent PPH with >90% success rates.

The current cost of the disposable Jada device (available only in the USA and Canada at US\$1200 each) puts it far out of reach of the low-income settings where most PPH deaths occur, leading to global inequity in care. In this study we will test an affordable suction tube uterine tamponade device to expand access to this life-saving technology.

South African Integrated Maternal and Perinatal Care Guidelines

Suction tube uterine tamponade with off-label use of the Levin stomach tube is included in the South African Integrated Maternal and Perinatal Care Guidelines (page 116 "Intra-uterine suction with NG tube (100mmHg)" and 117: "Consider a suction tube uterine tamponade as an alternative to balloon tamponade:

Observational comparative studies have shown that vacuum induced tamponade is 7x more effective than balloon tamponade")

https://knowledgehub.health.gov.za/system/files/elibdownloads/2024-10/Integrated%20Maternal%20and%20Perinatal%20Care%20Guideline 23 10 202 4_0.pdf

The U-STAT Device

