This application is an investigator-initiated, University-sponsored academic research program. Sinapi Biomedical are sub-contracted to supply the device. Sinapi manufactures a CE marked Ellavi balloon uterine tamponade system (Fig 1). The central tube is very similar to the Levin tube, but without the multiple suction holes, and served as the starting point for development of the U-STAT device.

Methods

This exploratory proof of concept (POC) clinical trial will build on our experience with our initial clinical studies of the improvised STUT device. This initial trial is designed to assess essential safety, performance, feasibility and acceptability and to give an indication of effectiveness and suitability for a substantive randomized effectiveness trial. It will include a limited number of participants (intervention arm n=40, control arm n=40).

Study type: Investigator-initiated, academic, non-commercial study.

Study Sponsor. Wits Health Consortium, a subsidiary of University of the

Witwatersrand

Study Design: Prospective intervention study

Study Sites: Frere/Cecilia Makiwane hospitals, South Africa

Study Duration: Four months

Study Population: Women 18 years old or more with risk factor(s) for PPH, for planned vaginal or caesarean birth; no serious medical conditions.

Inclusion Criteria

- Age 18 years and older
- Planned vaginal or caesarean birth
- One or more risk factors for PPH. These include
 - o Previous PPH
 - o Hypertension and pre-eclampsia
 - o Induction of labour
 - o Emergency caesarean birth
 - O Anaemia
 - Multiple pregnancy
 - Polyhdramnios
 - Macrosomia
 - Antepartum haemorrhage
- No serious medical conditions
- Provision of signed written informed consent

Intervention: Suction Tube Uterine Tamponade (STUT) using the purpose-designed soft plastic suction catheter inserted after vaginal birth or during caesarean birth. Low-pressure suction applied (approx. 100mmHg). Suction stopped after 30 minutes. If no further bleeding, tube removed. If bleeding resumes, suction continued. If bleeding not controlled within 20 min (or sooner if clinically indicated), proceed to further management according to local standard of care protocols (these might include additional uterotonics, tranexamic acid, compression methods, uterine balloon tamponade or laparotomy).

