- g. Did the suction tube remain in place in the uterus until removal (Yes/No/Unknown)
- h. Did the suction tube establish a good seal (no loss of suction) (Yes/No/Unknown)
- Did the suction tube interfere with or facilitate examination for and management of lower genital tract bleeding after vaginal birth (Facilitated/Interfered/Neither/not applicable/Unknown)
- j. Did the suction tube interfere with or facilitate surgical exposure during caesarean birth (Facilitated/Interfered/Neither/Unknown)
- k. Was there any blockage of the suction tube (Yes/No/Unknown)

Recruitment and consent

We plan to approach women at increased risk of PPH awaiting caesarean or induction of labour, pre-labour or in early labour and provide written and/or video information to them. They will be given time to discuss participation with friends and family and then invited to provide signed consent. Consent will be confirmed verbally immediately after birth, prior to device insertion.

Sample size

We aim to use the U-STAT in 40 participants, with a minimum of 25% being vaginal births and 25% caesarean section. 35 participants will provide 90% confidence that the true rate of adverse device effects and device deficiencies is under 10% (+/-10%). The sample is increased to 40 to account for any unexpected procedural difficulties in the first 5 recruits.

Procedures

Participating sites will be supplied with a 'PPH emergency trolley' containing all the supplies needed for STUT and emergency treatment of PPH, as well as forms for screening, enrolment, randomization and data collection. After vaginal birth, the suction tube will be inserted under sterile conditions transvaginally into the uterine cavity. Suction will be applied either with the manual suction device or with a surgical suction unit, set at 100mmHg suction pressure. If there is excessive bleeding which is not controlled by the STUT, the suction tube will be removed and management continued according to local protocols. If effective, the STUT suction will be interrupted every 30 minutes, and removed as soon as bleeding is controlled without suction. All other care will follow local practice. Blood loss will be measured from enrolment until bleeding is controlled (minimum 30 minutes), using a blood collection drape or Maternawell tray, plus blood collected in the UVT suction bottle, surgical suction and swabs.

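### The sample-size sentence presents what looks like a ±10-point precision figure as 90% assurance that the device-problem rate is under 10%; that assurance depends on the events seen

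*Protocol*

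**What the plan says.** The Outcomes section defines the target quantity: "The primary outcome is the combined frequency of adverse device effects and device deficiencies up to discharge from hospital". The definition is broad and takes in expulsion of the device, loss of suction pressure, blockage and user error.

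The Sample size section justifies the device arm in one sentence: "35 participants will provide 90% confidence that the true rate of adverse device effects and device deficiencies is under 10% (+/-10" percentage points). It then adds: "The sample is increased to 40 to account for any unexpected procedural difficulties in the first 5 recruits". It gives no formula, interval method, sidedness, expected rate or maximum number of events.

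The Data analysis section sets the reporting level: "For categorical variables, the number of participants, number of missing values and percentages will be reported, with 95% confidence intervals". The Methods section gives the planned size: "It will include a limited number of participants (intervention arm n=40, control arm n=40"). No p values are planned, and the protocol says that the study is not powered for formal comparison.

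**The concern.** The sentence makes two different statements at once. One is an upper bound: the true rate is below 10%. The other is a precision statement: the rate is known to within 10 points. An interval of 10% ± 10 points runs from 0% to 20%, so the second does not deliver the first.

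An upper bound is also a property of the data, not of the sample size. Thirty-five participants could support a rate under 10%, or rule it out, depending on the number of device problems.

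This is the only quantitative justification for the primary outcome, and in a study without tests the interval is the whole of the inference. An ethics committee, or those planning the later effectiveness trial, could take the protocol to promise a device-problem rate shown to be under 10%. The design gives that only if almost no participant has a device problem.

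**Working it through.** **Inputs from the protocol.** n = 35, raised to 40; confidence 90%; rate 10%; margin 10 points (Sample size). Reporting intervals 95% (Data analysis). Sidedness and method are not stated, so several are tried.

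**1. Reproducing 35 as a precision figure.** Plain Wald formula, n = z²p(1−p)/d² with p = d = 0.10:

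- 95% two-sided: 1.960² × 0.09 / 0.01 = 34.6, rounded up to 35.
- 90% two-sided: 1.645² × 0.09 / 0.01 = 24.3, rounded up to 25.

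Equivalently, at n = 35 the Wald half-width is 1.645 × √(0.09/35) = 8.3 points at 90% and 1.960 × √(0.09/35) = 9.9 points at 95%.

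Other methods at 90%, for a 10% rate:

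- Wald with continuity correction, z√(p(1−p)/n) + 1/(2n) ≤ 0.10: n = 34 (9.93 points; n = 33 gives 10.11).
- Exact (Clopper-Pearson) half-width, allowing a non-integer event count: 9.99 points at n = 33 and 9.67 at n = 35.
- One-sided exact limit below 20%: 20.04% at n = 34 and 19.84% at n = 35, so n = 35.

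So 35 is reproducible as ±10-point precision around 10%, at 95% by one formula and at 90% by others.

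**2. Testing the claim of a rate under 10%.** The exact one-sided 90% upper limit U after x events solves P(X ≤ x | n, U) = 0.10. For x = 0 this is U = 1 − 0.10^(1/n), giving 6.4% at n = 35 and 5.6% at n = 40.

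| Events | n = 35, exact | n = 35, Wilson | n = 40, exact | n = 40, Wilson |
|---|---|---|---|---|
| 0 | 6.4% | 4.5% | 5.6% | 3.9% |
| 1 | 10.7% | 9.1% | 9.4% | 8.0% |
| 2 | 14.5% | 13.0% | 12.8% | 11.5% |

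A direct check for one event, at a true rate of exactly 10%:

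- n = 35: P(X ≤ 1) = 0.9^35 + 35 × 0.1 × 0.9^34 = 0.025 + 0.097 = 0.122. This is above 0.10, so the limit exceeds 10%.
- n = 40: 0.9^40 + 40 × 0.1 × 0.9^39 = 0.015 + 0.066 = 0.080. This is below 0.10, so the limit is under 10%.

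With 2 of 35 every method tried gives more than 10%, including the uncorrected Wald limit (10.7%). With 2 of 40 only the uncorrected Wald limit falls below 10% (9.4%), and that approximation is poor with so few events.

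**3. What an observed 10% would show.** At n = 35 (3.5 events, interpolated) the exact two-sided 90% interval is about 3% to 22%. At n = 40, 4 events give an exact 95% interval of 2.8% to 23.7%. Neither excludes 20%.

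**4. At the reporting level.** With exact two-sided 95% intervals, the upper limit is 8.8% for 0/40 and 13.2% for 1/40.

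**5. How often the bound would be reached.** The protocol gives no expected rate, so these true rates are assumptions, and exact one-sided 90% limits are used.

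| Assumed true rate | 0 events in 35 | 0 or 1 event in 40 |
|---|---|---|
| 2% | 49% | 81% |
| 5% | 17% | 40% |

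**The case against.** The strongest reply is that this is an exploratory proof-of-concept study. It has no p values, no success threshold and no go/no-go rule at 10%, so the sentence decides nothing and the probabilities in step 5 treat it as a criterion that it is not. That stands, and it limits the severity. It does not make the sentence true.

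Several stronger readings are tempting, and the protocol does not support them:

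- *The figures 35, 90% and ±10 points cannot be reconciled.* This holds only for the uncorrected Wald formula. Other standard 90% methods give about 33 to 35.
- *90% is a slip for 95%.* The Wald match makes this plausible, but the protocol names no formula, so it cannot be asserted. A sizing level of 90% beside 95% reporting intervals is not in itself a contradiction.
- *A single event defeats the claim.* This is so for exact limits at n = 35. It is not so for Wilson limits at 35, nor for exact limits at the planned 40.
- *The first five recruits will be left out of the primary result.* The text only enlarges the sample on their account. The During recruitment section keeps participants in the trial on the intention-to-treat principle, and the outcome definition has no run-in exclusion.
- *The Synopsis means 20 per arm.* It speaks of testing the "affordable device among 40 consented participants at risk of postpartum haemorrhage following vaginal or caesarean birth" and adds a 1:1 control group. The Methods, Control and Ethics sections make 40 per group the evident intent.

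The last two are minor points of wording and no part of the error.

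**Conclusion.** The sentence is wrong as written and should be fixed. It offers what appears to be a ±10-point precision figure around a 10% rate as 90% assurance of a rate under 10%. With exact one-sided 90% limits, that assurance is reached only with 0 events in 35, or with 0 or 1 event in the planned 40. With Wilson limits at most 1 event is allowed at either size. If about 10% of participants have a device problem, a true rate of 20% is not excluded.

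The event-by-event limits rest only on the binomial model and the named method. The chances of reaching the bound rest also on assumed true rates of 2% and 5%. That the figure began as a precision calculation is an inference from the arithmetic, since the protocol does not show its working. The planned number of participants is not called into question.

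**What to change.** Replace the sentence with a statement of what the planned device arm delivers, naming the method and the confidence level. For example: *With 40 U-STAT participants, an observed rate of 10% (4/40) has an exact (Clopper-Pearson) 95% confidence interval of 2.8% to 23.7%. A one-sided exact 90% upper limit under 10% is reached only with 0 or 1 events (5.6% or 9.4%).*

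If the investigators prefer to keep a derivation of 35, they should give the formula, the sidedness, the assumed rate and the level, and present the result as precision only.

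Two optional clarifications can go into the same edit: say that all U-STAT participants, including the first five, count in the primary outcome, and give the Synopsis total as 80 (40 U-STAT and 40 control).

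The cost is wording only, with no extra participants and no change to the analysis. The stated assurance becomes less favourable.
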